#### 6.4.1.2 Primary outcome variables of tolerability.

- Burning
- Foreign body sensation

#### -Itching

-Eye comfort index

#### 6.4.1.3 Secondary outcome variables.

- Rupture time of the tear film
- Life signs: FC, FR, TAS.
- Subsequent segment
- Quality questionnaire.

#### 6.4.2 Efficacy variables.

6.4.2.1 Primary outcome variables.

Does not apply because it is a phase I study.

6.4.2.2 Secondary outcome variables.

Does not apply because it is a phase I study.

#### 6.4.3 Methods and scales to be used for the measurement of the variables

Variable	Unity	Symbol	Туре	Method of measurement	Normal value
Age	Years		Continuous	Calculation from the date of birth	NA
Gender	Female Male	F / M	Nominal	Direct questioning	NA
Adverse events	Number of cases	n	Discreet	Count	NA
Intraocular pressure	Milimeters of mercury	mmHg	Continuous	Goldman's applanation tonometry	11 - 21
Visual ability	Fraction	Snellen	Nominal	Primer	
Tear rupture time	Seconds	S	Continuous	Direct count	> 10
Eye comfort index	points		Discreet	Questionnaire	
Adverse events	Present / Absent		Nominal	Comprehensive valuation	Absent
Goblet cell density	Cells per square millimeter	Cel/mm 	Continuous	Cytology by impression	> 500 cel/mm 
Vital signs					
Heart rate	Beats per minute	lpm	Discreet	Auscultation	60 - 100
Breathing frequency	Breaths per minute	rpm	Discreet	Auscultation	12 – 24
Systemic blood pressure	Milimeters of mercury	mmHg	Continuous	Non-invasive auscultatory measurement	< 120 / 80
Previous segment					
Epithelial defects	Degrees		Discreet	Direct observation with fluorescein and green lysamin stain	Oxford Scale

Sophia Laboratories, S.A. of C.V.

Variable	Unity	Symbol	Туре	Method of measurement	Normal value
Ophthalmologic signs ar	nd symptoms				
Conjunctival hyperemia	Normal / Very Light / Mild / Moderate / Severe		Ordinal	Direct observation. Classification of Efron.	Normal
Chemosis	Present / Absent		Nominal	Direct observation	Absent
Burning	Severity: Absent, very mild, mild, moderate and severe		Nominal	Direct questioning	Absent
Foreign body sensation	Severity: Absent, very mild, mild, moderate and severe		Nominal	Direct questioning	Absent
Pruritus	Frequency: At all times, almost at all times, 50% of the time, almost in no time, at any time		Nominal	Direct questioning	Absent
Postinstilation symptoms	5				
Burning	Present / Absent		Nominal	Journal of the subject	Absent
Foreign body sensation	Present / Absent		Nominal	Journal of the subject	Absent
Pruritus	Present / Absent		Nominal	Journal of the subject	Absent
Red eye (symptom)	Present / Away		Nominal	Journal of the subject	Absent

Sophia Laboratories, S.A. of C.V.

Variable	Unity	Symbol	Туре	Method of measurement	Normal value
Posterior segment					
Magula	Normal /				
Macula	Abnormal		Nominal	Observación directa	Normal
Optical disk integrity	Normal / Abnormal		Nominal	Observación directa	Normal
Blood count					
Erythrocytes		M/uL	Continuous		
Hemoglobin	Grams over deciliter	g/dL	Continuous		
Hematocrit	Percentage	%	Continuous		
VGM	Femto liters	fL	Continuous		
НСМ	picograms	pg	Continuous		
CMHbG	Grams over deciliter	g/dL	Continuous		
Leukocytes	Thousands per liter units	Mil/uL	Continuous		
Platelets	Thousands per liter units	Mil/uL	Continuous		
Myelocytes	Percentage	%	Discreet		
Metamyelocytes	Percentage	%	Discreet		
Bands	Percentage	%	Discreet		
Segmented	Percentage	%	Discreet		
Lymphocytes	Percentage	%	Discreet		
Monocytes	Percentage	%	Discreet		
Eosinophils	Percentage	%	Discreet		
Basophils	Percentage	%	Discreet		
Blastos	Percentage	%	Discreet		
Blood chemistry					
Glucose	Milligrams on deciliter	mg/dL	Continuous		
Urea	Milligrams on deciliter	mg/dL	Continuous		
Creatinine	Milligrams on deciliter	mg/dL	Continuous		
Liver function tests					

Variable	Unity	Symbol	Туре	Method of measurement	Normal value
Alanine transferase	Units on liter	U/L	Continuous		
Aspartate transferase	Units on liter	U/L	Continuous		
Total bilirubin	Milligrams on deciliter	mg/dL	Continuous		
Direct bilirubin	Milligrams on deciliter	mg/dL	Continuous		
Indirect Bilirubin	Milligrams on deciliter	mg/dL	Continuous		

Table 5. Scales to be used.

The following describes the methods and scales that will be used for the measurement of the variables, which are in strict alphabetical order:

# 6.4.3.1 Visual ability.

Visual acuity (VA) is a test of visual function. Spatial visual acuity is the ability to distinguish separate elements of an object and identify them as a whole. It is quantified as the minimum separation angle (located at the nodal point of the eye) between two objects that allows perceiving them as separate objects.

Snellen's notation is described as the distance at which the test is performed, divided by the distance at which the letter is vertically equivalent to 5 arc minutes. Thus, at 6 meters a letter 6/6 (20/20) equals 5 minutes of arc, a letter 6/12 (20/40) equals 10 minutes, and a letter 6/60 (20/200) equals 50 minutes The Snellen fraction can also be expressed as a decimal (ie 20/20 = 1 and 20/40 = 0.5). [38]

The VA will be evaluated basally, without refractive correction with the Snellen chart. Which will be located in a place with adequate lighting, natural or artificial and at a distance of 3m from the subject to be evaluated. The visual acuity of each eye will be taken, starting with a right eye (DO) asking the subject to keep both eyes open and using an occluder to cover the left eye (OS); the subject will read aloud the lines that the evaluator points out, the line of smaller letters that he reaches to see will be annotated by the fractional evaluator as the DO of the DO in the clinical record. Proceed to the OS with the same method.

Subsequently the best refractive correction of the subject will be made and the examination will be repeated using the obtained refraction. This result will be reported as CV, it will be written in fraction in the clinical file and in the CRF, in addition in the CRF it will be written in decimal. By definition, the CV can not be inferior to the AV.

#### 6.4.3.2 Goblet cell density (Cytology per impression).

The density of goblet cells in the conjunctiva can be a reflection of the severity of alteration in the ocular surface. [39] It has been determined that the normal density is greater than 500 cel / mm2. [40] Impression cytology refers to the application of a cellulose acetate filter to the ocular surface to remove the superficial layers of the epithelium; these removed cells can be subjected to histological, immunohistological or molecular analysis. [41]

The cytology per impression of the conjunctiva will be done by the researcher using the device provided by the sponsor for this purpose, which may consist of a circular cell of approximately 10 mm in diameter, with a cellulose acetate filter millicell. After ocular surface anesthesia, with topical Sophia Laboratories, S.A. of C.V.

tetracaine, the researcher will ask the subject to expose the temporal surface of the eye to be evaluated and gently press the cell on the temporal conjunctiva (2 to 3 mm of the sclerocorneal limbus) for 5 seconds and remove the cell with a peeling technique (Illustration 1. Cytology per impression). Immediately fix with diethyl ether spray with one or two shots at 15 cm distance. The investigator will contact the Courier designated by the sponsor for the delivery of the samples to the histopathological analysis.

The data of the histopathological report to be recorded in the CRF are: density of goblet cells and degree of squamous metaplasia according to the Nelson scale. (See Table 6)

In the visits that are required to perform this procedure, it will be done prior to the use of ocular surface stains.

Illustration 1. Cytology per impression.

Grade	Detail description of the epithelial cells	Characteristics of goblet cells
0	Small and round cells; Large nuclei, 1: 2 ratio with nuclear cytoplasm	Abundant goblet cells (> 500 cells / mm2), globose and oval with an intense PAS-positive staining of the cytoplasm.
1	Slightly enlarged cells; smaller nuclei, 1: 3 ratio with nuclear cytoplasm	Marked decrease in the number of goblet cells (350 to 500 cells / mm2) but still maintain their globose and oval shape and intense staining
2	Enlarged and polygonal cells; small nuclei, ratio 1: 4 to 1: 5 with nuclear cytoplasm	Marked decrease in the number of goblet cells (100 to 350 cells / mm2), less intense PAS - positive with poorly defined cell borders
3	Even larger and polygonal cells; small and pyknotic nuclei, 1: 6 ratio with nuclear cytoplasm	Few goblet cells (<100 cells / mm2)
Adapted	from Nelson & Wright [24] [42]	

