#### 6.4.3.10 Breaking time of the tear film.

One of the first aspects of the tear film that changes when there is an alteration to the ocular surface, is its stability. In general, if the corneal or conjunctival surface is damaged, it is unlikely that a stable tear film can be maintained.

The most common method to evaluate the stability of the tear film is the evaluation of TRL with fluorescein. Once the fluorescein is instilled, with the cobalt blue filter the patient is asked not to blink. The precorneal colored fluorescein layer will change to less fluorescent or non-fluorescent

regions. The time that elapses from the last blink until the appearance of these regions is the TRL. It will be reported in seconds, in the clinical file and in the CRF.

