# 6.5 6.5 Timeline and study diagram.

Procedures	Scrutiny	Basal Visit	Visit 1	Visit 2	Final Visit	Call Security
i loccuares		Day 0	Day 3 ± 1	Day 6 ± 1	Day 11 ± 1	Day 13 ± 1
CI Signature	Х					
Clinic history	Х					
Ophthalmological clinical history	Х					
Laboratory sample taking	Х				Х	
Laboratory tests review		Х				х
Pregnancy test	Х				Х	
Eligibility criteria	Х	Xa				
Assignment		Х				
Delivery of intervention		Х	Х	Х		
Return of intervention			Х	Х	Х	
Adherence evaluation			Х	Х	Х	
Adverse events			Х	Х	Х	Х
Intraocular pressure	Х	X1	Х	Х	Х	
Visual ability	Х	X1	Х	Х	Х	
TRL	Х	X1	Х	Х	Х	
Epithelial defects (TF and TVL)	Х	X1	Х	Х	Х	
Eye signs and symptoms	Х	X1	Х	Х	Х	
posterior segment	Х	X1			Х	
Vital signs	Х	X1	Х	Х	Х	
Ocular Comfort Index		Х			Х	
Goblet cell density (cytology by impression)		х			х	
Daily delivery of the subject		Х	Х	Х		
Return / Evaluation of the subject's Journal			Х	Х	х	
Delivery Quality Questionnaire		Х				
Return and Evaluation of the quality questionnaire					Х	
Continuity evaluation of the subject			Х	Х		

a The eligibility criteria will be completed with the revision of the laboratory exams. 1 These measurements may be taken from the result of the screening visit, if it does not exceed the previous 7 days. It is the prerogative of the PI to decide whether to repeat the measurements at the baseline visit.

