- Evaluation of variables: The data of the evaluation of the variables listed below can be taken from the scrutiny visit, as long as it does not exceed 7 days prior to this visit. It is the prerogative of the IP to decide whether to use the information from the screening visit or to repeat the evaluations in this visit.
  - Intraocular pressure
  - o Visual capacity
  - TRL
  - Epithelial defects
     Eye signs and symptoms

- Subsequent segment
- vital signs
- Eye comfort index: see 6.4.3.3 Eye comfort index
- Density of goblet cells (cytology per impression): see 6.4.3.2 Density of goblet cells (cytology per impression)
- Delivery of the subject's diary: It refers to the delivery by the IP to the subject, the subject's daily instrument.
- Delivery of quality questionnaire: It refers to the delivery by the IP to the subject, the quality questionnaire instrument.

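### Final-visit staining and break-up time always follow impression cytology, but their baselines may be copied from a cytology-free screening visit, so within-group change can include a procedural effect

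*Combined protocol and SAP*

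**What the plan says.** Section 6.4.3.2 describes impression cytology as a filter applied "to remove the superficial layers of the epithelium". The device may be "a circular cell of approximately 10 mm in diameter", pressed on the temporal conjunctiva. On order the section is explicit: whenever cytology is scheduled, "it will be done prior to the use of ocular surface stains". TRL is read with fluorescein (6.4.3.10), so it falls under the same rule.

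The schedule in section 6.5 and the visit lists in 6.4.4 place cytology at the basal and final visits only. Staining and TRL are measured at screening, basal, Visit 1, Visit 2 and final.

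For the basal visit, footnote 1 to the schedule says of a set of items that includes TRL and the epithelial defects: "These measurements may be taken from the result of the screening visit, if it does not exceed the previous 7 days". Section 6.5.1.2 repeats the permission and leaves it to the investigator: "It is the prerogative of the IP to decide whether to use the information from the screening visit or to repeat the evaluations in this" (that is, at the basal visit).

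Section 5.5.2 lists changes in ocular surface stains and in TRL among the specific objectives. Section 6.4.1 makes epithelial defects of cornea and conjunctiva a primary safety variable and TRL a secondary one. Section 8.3.1 plans a within-group Wilcoxon test and a between-group Kruskal-Wallis test at 0.05 for continuous quantitative variables, and judges PRO-087 safe and tolerable by comparison with the other arms.

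**The concern.** A change score is interpretable only if both ends are measured under the same conditions. Here the final value always comes after an imprint. The baseline comes after an imprint for some subjects and not for others, and the investigator chooses which. The plan gives no recovery interval between cytology and staining, does not exclude the sampled area from Oxford grading, and makes no adjustment.

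The documents themselves suggest the likely direction. Cytology removes epithelium, and 6.4.3.10 states that "if the corneal or conjunctival surface is damaged, it is unlikely that a stable tear film can be maintained". A subject with a copied baseline may therefore show more staining and a shorter TRL at the final visit for reasons unrelated to the drop. At stake is the within-group account of ocular surface safety: the report could describe worsening on PRO-087, and on both comparators, that the study procedure produced.

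**Working it through.** The plan states no figure on this point, so there is none to reproduce. The check is a comparison of visits, followed by an illustration of size.

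**Step 1. Conditions at each visit** (6.4.3.2, 6.4.4, 6.5 and footnote 1, 6.5.1.2)

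| Value | Cytology before staining and TRL? |
|---|---|
| Screening | No |
| Baseline, copied from screening | No |
| Baseline, repeated at the basal visit | Yes |
| Visits 1 and 2 | No |
| Final | Yes |

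**Step 2. What each change contains.** Code values so that higher is worse. Let D be the drug effect, c the imprint effect and f the share of subjects with a copied baseline. Assume c is the same at the basal and final visits within a subject.

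- Baseline repeated: (D + c) − c = D.
- Baseline copied: (D + c) − 0 = D + c.
- Arm average of baseline-to-final change: D + f × c.
- Visit 1 or 2 against a repeated, post-cytology baseline: D − c, a tilt toward improvement.
- Visit 1 or 2 against a cytology-free screening value: D.

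**Step 3. Illustration on a grade scale.** Assumptions, none from the documents: no drug effect; random one-grade noise of 10% each way; the imprint raises the grade by one in a given share of subjects; n = 10; exact two-sided Wilcoxon at 0.05. Six rises of one grade with no falls give p = 2 × 0.5^6 = 0.031. Five give 2 × 0.5^5 = 0.0625, so at least six consistent rises are needed. By simulation, the chance that an arm shows significant worsening is:

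| Imprint raises grade in | All baselines copied (f = 1) | Each copied with probability one half (f = 0.5) |
|---|---|---|
| 25% of subjects | about 3% | about 0.3% |
| 50% | about 27% | about 3% |
| 75% | about 73% | about 11% |

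Section 6.6.1 says both eyes enter the analysis, and the plan does not specify the exact test. With 20 eyes per arm treated as independent and the normal approximation, f = 0.5 gives about 13%, 36% and 66%.

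**Step 4. Illustration on a continuous scale, as for TRL.** Change is normal with SD 1 and no drug effect. A shift of s SD toward worsening is added for copied baselines (2,000 runs, n = 10). The within-group Wilcoxon rejection rate is:

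| s | f = 1 | f = 0.5 |
|---|---|---|
| 0.25 | 11% | 6% |
| 0.5 | 28% | 11% |
| 1.0 | 79% | 23% |

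With f = 0 it is about 5%.

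**Step 5. Between arms.** In the Step 4 simulations the Kruskal-Wallis rejection rate stays at about 4% to 6% throughout, because every arm receives the same mixture. What remains is added variance, f(1 − f)s². With f = 0.5 and s = 1 this is 0.25, so the SD of change rises from 1 to √1.25 = 1.12. With s = 0.5 it is 0.0625, an SD of 1.03.

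**The case against.** Four points against the concern carry weight.

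- Copying is optional and limited to values no more than 7 days old. Where the tests are repeated at the basal visit, the order rule already puts cytology first at both ends and the values match. This stands: the problem is conditional on copying. A reader might infer that all baseline-to-final changes are biased, and the documents do not support that.
- The safety rule in 8.3.1 compares PRO-087 with its comparators, and all arms share the procedure. This stands. A reader might infer that the artefact could by itself make PRO-087 look worse than its comparators. It could not do so systematically. A reader might also infer that uneven copying across arms is a source of bias. But the investigator is blinded (7.4) and allocation is random, so imbalance in copying arises by chance and counts as noise.
- Section 8.3.1 assigns Wilcoxon to continuous variables, and Table 5 types epithelial defects as discrete. This stands: the test is explicit for TRL, while for the Oxford grade it is an inference, so Step 3 is illustrative.
- The mechanism is partly inferred. Section 5.1 calls cytology minimally invasive, 6.4.3.2 describes gentle pressure for 5 seconds, TRL reads the film over the cornea while the imprint is on the temporal conjunctiva, and the plan gives an order but no interval. Topical anaesthetic precedes staining at every visit, so tetracaine is not a clear difference. This limits certainty about the size, especially for TRL. It does not remove the mismatch in conditions.

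**Conclusion.** The concern holds in conditional form. For every subject whose baseline staining and TRL are copied from screening, baseline-to-final change compares a value without an imprint with a value after one. Within-group change in a primary and a secondary outcome then contains f × c in addition to any drug effect, probably toward worsening.

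The size cannot be fixed from the documents, which give neither the imprint effect nor the share of copied baselines. In the one-grade model it runs from negligible (0.3%, with half the baselines copied and an imprint effect in 25% of subjects) to severe (73%, with all copied and an effect in 75%). The upper figures are a worst case and should not be quoted without the full-copying assumption.

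The between-arm conclusion on safety is not systematically biased. It gains some noise, which is unhelpful under a rule that treats absence of a difference as safety, but in the continuous model with half the baselines copied the rise in SD was only 3% for s = 0.5 and 12% for s = 1. This is a cheap improvement to within-group interpretation and does not invalidate the design.

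**What to change.** 1. Remove TRL and epithelial defects (TF and TVL) from the items covered by footnote 1 in section 6.5 and from the reuse list in 6.5.1.2, and align the matching permission in 6.4.4. Measure both at the basal visit in every subject, in the same order relative to cytology as at the final visit, and use that value as the reference for final-visit change.
2. Keep the cytology-free screening value, which every subject already has, as the reference for change at Visits 1 and 2. Without this second step the first would tilt day-3 and day-6 changes toward improvement and could mask early harm. State whether the screening value still serves when it is more than 7 days old.
3. Optionally, record the Oxford grade by zone and add a sensitivity analysis that leaves out the temporal imprint zone. Keep the full grade as primary, so that no part of the conjunctiva is lost from a primary safety outcome.

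The cost is a few minutes of repeat staining for subjects whose values would have been copied, with dyes already in use, and two clearly labelled baselines in the dataset. Step 3 adds a small CRF change, since 6.4.3.4.1 now records one Oxford value per stain.

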# 6.4.3.3 Eye comfort index.

It is a questionnaire designed to measure the irritation of the ocular surface with Rasch analysis to produce estimates on a linear scale of intervals (ratings: 0-100). Similar to the index for ocular Sophia Laboratories, S.A. of C.V.

surface diseases, the ocular comfort index (ICO) evaluates symptoms. The ICO contains 8 items (one positive and eight negative) that focus on the discomfort associated with alterations of the ocular surface. Each of these questions has two parts, which inquire separately the frequency and severity of the symptoms. [43] See annex 13.1 Eye comfort index.

The evaluator will deliver the questionnaire to the subject and allow the subject to answer it calmly without any pressure and / or coercion, will only assist him if he has difficulty understanding any of the questions.

#### 6.4.3.4 Eye surface integrity:

This will be done by means of biomicroscopy using the slit lamp of the research center. A full assessment of the previous segment will be made, which will be recorded in the clinical file. The lighting techniques used will be at the discretion of the IP.

The variables that will be registered in this protocol are:

#### - Conjunctival hyperemia.

It is defined as the simplest reaction of the conjunctiva to a stimulus, a red appearance secondary to the vasodilation of the conjunctival vessels of variable intensity. He will graduate using the Efron scale. [44] See annex 13.2 Efron scale for conjunctival hyperemia - *Chemosis.* 

It is defined as conjunctival edema, the result of an inflammatory reaction. It is qualified as present or absent. The evaluator will use a narrow beam of light at 60 ° and will measure if the conjunctiva separates from the sclera at  $\geq 1/3$  of the total palpebral opening or if it exceeds the gray line. [45]

#### 6.4.3.4.1 Stains.

#### • Staining with green lysine.

A drop of topical anesthetic will be instilled in the conjunctival cul-de-sac, then a second drop will be applied to the tip of the strip of green lysine and it will be allowed to slip towards the bottom of the sac. It is essential to quickly evaluate the staining, in sequence, first in the DO and then the OS, so that the observed patterns are equally bright. [19] See Annex 13.3 Oxford Scale

#### • Fluorescein staining.

A drop of topical anesthetic will be instilled into the conjunctival cul-de-sac, then a second drop will be applied to the tip of the fluorescein strip and it will be allowed to slip to the bottom of the sac. It is essential to quickly evaluate the staining, in sequence, first in the DO and then the OS, so that the observed patterns are equally bright. This valuation will be made with the cobalt blue filter. [19] See Annex 13.3 Oxford Scale

For both stains, the value obtained according to the Oxford scale will be registered in the CRF.

#### 6.4.3.5 Presence of adverse events.

The management of the EAs will be done according to what is described in section 9.3 Adverse events

The PI will register in the corresponding section of the CRF the EAs that come to present the subjects of the study in addition to referring it in its essential document.

